CONTROL PRODUCT, DOSE AND ROUTE OF ADMINISTRATION	The mRNA-1273 vaccine, provided as a sterile liquid at a concentration of 0.2 mg per milliliter, will be administered by injection into the deltoid muscle in a volume of 0.25 ml (50 ug), 0.5 ml (100 ug) or 1.0 ml (200 ug). Vaccine mRNA-1273 will be stored at 2° to 8°C (35.6° to 46.4°F) at clinical sites before preparation and vaccination. No dilution was required. Doses could be held in syringes for up to 8 hours at room temperature before administration.
DURATION OF PARTICIPANT PARTICIPATION AND DURATION OF STUDY	
Treatment: Day 1 intramuscular injection
 
Follow-up: 6 months
 
Participants will be on study for up to 7 months.
 
The total duration of the study for recruitment and completion of participants is expected to be up to 12 months.

CONCOMITANT MEDICATIONS	Based on inclusion criteria, participants will be required to be on a regimen of triple immunosuppression including prednisone, mycophenolate mofetil (minimum 250 mg bid) or mycophenolate sodium (minimum 180 mg bid), and tacrolimus at the Day 1 study visit. Participants receiving IVIG or augmented immunosuppression for treatment of acute cellular rejection or antibody mediated rejection will be excluded from the study.
EFFICACY EVALUATIONS	
PRIMARY ENDPOINT	
 1. Frequency and grade of each solicited local and systemic reactogenicity AE will be recorded on a daily diary using the FDA Toxicity Grading Scale and collected from Day 1 until Day 7. 2. Frequency and grade of each unsolicited adverse events will be recorded on a daily diary and collected from Day 1 until Day 30.

	
3. Frequency of any serious adverse experiences (SAEs) and adverse events of special interests (AESIs) will be collected from Day 1 until Day 180.

SECONDARY ENDPOINTS	
1. Humoral immunogenicity measured by anti-RBD and anti-spike (S-2P) IgG levels at Day 30.
 
2. Humoral immunogenicity measured by neutralizing antibody titers from a pseudovirus neutralization assay at Day 30.
 
3. Cellular immunogenicity measured by cellular response assays including flow cytometry with intracellular staining at Day 30.

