2 STUDY RATIONALE

In contrast to immunocompetent participants in vaccine trials, solid organ transplant recipients have poor responses to SARS-CoV-2 vaccines with studies reporting anti-S-protein antibody detection in only 34–

54% after the second dose (11–13). Lung transplant recipients in particular have weak responses to the vaccine with antibody responses observed in less than 20% after the second dose (11, 14–16). Due to the allograft's exposure to the external environment and active immune surveillance, lung transplant recipients generally require higher levels of immunosuppression. Lung transplantation is also unique among the solid organ transplants in the direct infection and injury of the allograft by SARS-CoV-2.

Thus, lung transplant recipients have had poor outcomes after COVID-19 infection with case fatality rates ranging between 14–39% (17–20). Third vaccine doses appear to improve immune responses for solid organ recipients (21–23), but has not been studied specifically for lung transplant recipients.

The objectives of this study are to determine the safety, reactogenicity and immunogenicity of a mid-dose (100 ug) and high-dose (200 ug) booster mRNA-1273 vaccine among lung transplant recipients who previously received three or four mRNA-1273 vaccine doses.

A single-center observational cohort study of 165 pts at UCLA found that only 35% of lung transplant recipients mounted an anti-RBD IgG antibody response after the second mRNA vaccine dose (Pfizer or Moderna), with an increase to 59% after the third dose. In contrast, lung transplant recipients who were either: 1) infected with COVID-19 or 2) received at least one vaccine dose before transplant, had higher antibody levels approaching those of healthy participants. This suggests that lung transplant recipients may be able to mount a stronger immune response to higher antigen exposure, and may be able to retain their antibody response afterwards. Importantly, we found that reactogenicity was significantly less for lung transplant recipients after both the second and third dose of the vaccine compared with healthy vaccine recipients. The frequency of any systemic adverse reaction (fever, fatigue, headache, myalgia, arthralgia, chills or nausea) was 46% after the third dose for lung transplant recipients compared with 80% for healthy vaccine recipients.

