Lung transplant recipients, due to their immune suppression medicines, have had weak responses to the COVID-19 vaccines with antibody responses noted in less than 20% after the second vaccine dose (16–18). Lung transplantation is also unique among the solid organ transplants in the direct infection and injury of the allograft by SARS-CoV-2. Thus, lung transplant recipients have poor outcomes following COVID-19 infection with a high mortality rate. Third dose vaccines appear to improve immune responses for solid organ recipients, but has not been studied specifically for lung transplant recipients.

The current CDC guidance is for moderately or severely immunocompromised patients to receive a 50 ug booster: 1) At least 3 months after 3rd dose (first booster), and 2) At least 4 months after 4th dose (2nd booster). We believe that this dosing will be insufficient for many lung transplant recipients, particularly in those who did not receive any vaccine doses prior to their lung transplant, and leave them at high risk of poor COVID-19 outcomes. Importantly, due to their immunosuppression, lung recipients appear to have decreased side effects and reactogenicity to the SARS-CoV-2 vaccine.

We hypothesize that a 100 ug mid-dose and 200 ug high-dose mRNA-1273 booster dose can be safely administered to lung transplant recipients who previously received all of their vaccine doses after their lung transplant. We further hypothesize that the higher dose boosters will induce a stronger immune response to SARS-CoV-2 as measured by humoral and cellular response assays. The objectives of this study are to test these two hypotheses.

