4 STUDY DESIGN

4.1 Study Overview

This is a Phase I/II open-label dose-finding trial among lung transplant recipients who received three or four mRNA vaccine doses (mRNA-1273 or BNT162b2) after lung transplantation to: standard-dose (50 ug), mid-dose (100 ug) or high-dose (200 ug) mRNA-1273 booster vaccine. Participants will be enrolled into three dose groups: 1) Standard-dose (50 ug) – 20 participants, 2) Mid-dose (100 ug) – 20 participants, 3) High-dose (200 ug) – 20 participants. The first 2 participants in both the mid-dose and high dose groups will be considered the ‘sentinel’ group. Participants in the sentinel group will receive the vaccine and undergo a 7-day observation period for safety and reactogenicity before additional participants are enrolled into that dose group.

Overall study enrollment will begin with the mid-dose sentinel group (n=2). During the observation period for the mid-dose sentinel group, we will enroll two participants into the standard-dose group. Once the mid-dose sentinel group completes their 7-day observation period without triggering halting rules and is approved to proceed by the DSMB, we will enroll the next 27 participants (Cohort 1) with a 2:1 randomization into the mid-dose (n=18) and standard-dose (n=9) groups.

Once all 20 participants have received their mid-dose vaccine without triggering halting rules and is approved to proceed by the DSMB, we will enroll the high-dose sentinel group (n=2). Once the high-dose sentinel group completes their 7-day observation period without triggering halting rules and is approved to proceed by the DSMB, we will enroll the next 27 participants (Cohort 2) with a 2:1 randomization into the high-dose (n=18) and standard-dose (n=9) groups. Thus, all 20 participants in the mid-dose group will be enrolled prior to enrollment of the high-dose group.

We will perform stratified randomization for the two cohorts based on: 1) the number of prior doses, and 2) prior receipt of any BNT162b2 vaccines. Randomization will be done by the UCLA Clinical and Translational Science Institute (CTSI) statistics team based on scheduled participants prior to the study visit. The 6 participants in the sentinel (n=4) and initial (n=2) groups (Table 1) will be assigned into the 3 groups based on their scheduled visit day.

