14 STATISTICAL METHODS AND CONSIDERATIONS

14.1 General Considerations

Data collected in this study will be presented using summary tables and participant data listings. Continuous variables will be summarized using descriptive statistics, specifically the mean, median, standard deviation, minimum, and maximum. Categorical variables will be summarized by frequencies and percentages. Data Sets Analyzed:

- **Intent-to-Treat (ITT) Analysis Set**

The ITT analysis set includes all participants who are enrolled into a treatment (dose) group regardless of whether participants receive any study drug(s), or receive a different regimen from the regimen they were randomized to. Participants will be assigned into a dose group as described above.

- **Safety Analysis Set**

A safety analysis set will include data from participants who receive at least one dose of study treatment, with treatment assignments designated according to the actual treatment received. This analysis set will be used in the analyses of safety variables (primary endpoint) as well as study treatment administration.

- **Per-Protocol (PP) Analysis Set**

The PP analysis set includes data from participants in the ITT analysis set who meet the general criteria defining the target population for this study, are adherent to the protocol, are compliant with study drug treatment, and are evaluable for relevant efficacy endpoints. Treatment assignment will be designated according to the actual treatment received. The PP analysis set will be used in the analyses of the secondary endpoints. The PP analysis set will only include participants randomized to the dose-group (Cohorts 1 and 2, Figure 1). The PP analysis set will exclude participants in the sentinel mid-dose (n=2), sentinel high-dose (n=2) and initial standard-dose groups (n=2) who were not randomized to their dose-group. Participants who are found to have detectable anti-N-protein IgG antibody levels (representing prior infection) at their Day 1 (baseline) visit will be excluded from the PP analysis set.

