14.4 Analysis of Secondary Endpoints

- Binding antibody:** The anti-RBD and anti-spike (S-2P) IgG concentrations (log10 and geometric mean concentrations (GMC)) at Day 30 will be evaluated with comparisons between the standard-dose versus high-dose groups. T-tests with two-sided $p<0.05$ significance will be used (overall α level of 0.1). Changes in the anti-RBC and anti-spike IgG concentrations at Day 30 will be compared between the standard-dose versus high-dose groups using two sample T-tests with two-sided $p<0.05$ significance (overall α level of 0.1). The percent of participants with detectable antibody levels (greater than the LLOQ) at Day 30 will also be evaluated using Fisher's exact tests. Pairwise comparisons of binding antibodies will also be evaluated between the standard-dose versus mid-dose groups.
- Neutralizing antibody:** Neutralizing antibody titers (geometric mean titers (GMT)) from a pseudovirus neutralization assay at Day 30 will be compared between the standard-dose versus high-dose groups using T-tests with two-sided $p<0.05$ significance (overall α level of 0.1). Changes in the neutralizing antibody titers at Day 30 will be compared between the standard-dose versus high-dose using two sample T-tests with two-sided $p<0.05$ significance (overall α level of 0.1). The percent of participants with detectable neutralizing antibody levels (greater than the LLOQ) at Day 30 will also be evaluated using Fisher's exact tests. Pairwise comparisons of neutralizing antibodies will also be evaluated between the standard-dose versus mid-dose groups.

3. **Cellular immunogenicity:** The change in the frequency of target cytokine producing T-cells by flow cytometry with intracellular staining at Day 30 will be compared using the Kruskal-Wallis Test for the standard-dose versus high-dose groups. A comparison of T-cell frequencies between the standard-dose versus high-dose groups will be evaluated using the Wilcoxon rank-sum test. Pairwise comparisons of cellular immunogenicity will also be evaluated between the standard-dose versus mid-dose groups.

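### The immunogenicity tests pool standard-dose controls from two sequential cohorts with no cohort, baseline or stratum term; the concurrent 18 v 9 estimate should be prespecified as a sensitivity analysis beside an adjusted pooled one

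*Combined protocol and SAP*

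**What the plan says.** Enrolment is sequential. Under 4.1, "all 20 participants in the mid-dose group will be enrolled prior to enrollment of the high-dose group". Cohort 1 randomises 18 mid-dose and 9 standard-dose participants. Then, after the high-dose sentinels and DSMB approval, "we will enroll the next 27 participants (Cohort 2) with a 2:1 randomization into the high-dose (n=18) and standard-dose (n=9) groups". Randomisation is described as "stratified randomization for the two cohorts based on: 1) the number of prior doses, and 2) prior receipt of any BNT162b2 vaccines".

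The secondary endpoints use the per-protocol (PP) set, and 14.1 says "The PP analysis set will only include participants randomized to the dose-group (Cohorts 1 and 2, Figure 1". The standard-dose group is therefore 9 + 9 = 18, which matches the n given in 12.3. The plan never uses the word pooled; pooling follows from this group definition.

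In 14.4, "Changes in the anti-RBC and anti-spike IgG concentrations at Day 30 will be compared between the standard-dose versus high-dose groups using two sample T-tests" (the first analyte is evidently anti-RBD). Day 30 levels are also t-tested, detectability is compared by Fisher's exact test, and cellular responses by rank tests. Each is repeated for standard v mid. Section 5.2 and the synopsis repeat the plan. None of the three names a cohort term, a baseline covariate, a stratum or a concurrent-control analysis; baseline enters only by subtraction, in the tests of change.

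**The concern.** The sponsor limits the PP set to randomised participants, yet half the controls in the high v standard contrast were randomised in a different cohort, against a different dose and at an earlier time. All 18 satisfy the PP rule; the gap is that 9 of them are not concurrent.

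Stratified randomisation balances arms within a cohort. It does not balance Cohort 1 controls against Cohort 2 high-dose recipients. Change scores remove a shift in pre-dose level but not a shift in response to the vaccine, and the Day 30 level and detectability tests do not use baseline at all.

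There are plausible routes for drift. The guidance cited in Section 2.1 reads "receive a 50 ug booster: 1) At least 3 months after 3rd dose (first booster), and 2) At least 4 months after 4th dose", so the mix of three- and four-dose recipients may move with calendar time. The interval since the last dose has a minimum of 4 months but no maximum. Infection between Day 1 and Day 30 is not screened out.

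At stake is the contrast on which the trial is sized. Positive drift would favour the high dose and negative drift would hide its effect.

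**Working it through.** **Inputs from 14.6.** Expected log10 rises are 0.91 (200 ug) and 0.23 (50 ug), so the difference is 0.68; SD 0.63; two-sided 0.05; 80% power.

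**The plan's own figure.** Noncentral-t power is 78.5% at 14 per group and 81.4% at 15. The stated minimum of 15 is reproduced.

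**Power with the randomised PP numbers (no drift).** SE = 0.63 × √(1/n₁ + 1/n₂).

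| Comparison | SE | Power at 0.68 |
|---|---|---|
| Pooled, 18 v 18 | 0.210 | 88.2% |
| Concurrent, 18 v 9 (t-test, 25 df) | 0.257 | 71.9% |
| Dose + cohort model on all 54 (50 df) | 0.257 | 73.7% |

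**Bias.** Let d be the extra Cohort 2 response not due to dose. The pooled control mean carries (9 × 0 + 9 × d)/18 = d/2. High-dose participants all carry d, and mid-dose participants carry 0. High v standard is therefore biased by d - d/2 = +d/2, and mid v standard by 0 - d/2 = -d/2. This is exact for differences in means or proportions with equal evaluable controls per cohort. Rank tests shift in the same direction, but not by a literal half.

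**Effect on the pooled t-test (simulation, SD 0.63).** The values of d are assumptions.

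| Size of d | Rejection, no dose effect, +d | Power at 0.68, -d |
|---|---|---|
| 0.1 | about 5.6% | about 83% |
| 0.2 | about 7.3% | about 76% |
| 0.3 | about 10.1% | about 68% |

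The concurrent test rejects about 5% throughout and keeps about 72% power.

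**Mean squared error.** Pooled: 0.63² × (2/18) + d²/4 = 0.0441 + d²/4. Concurrent: 0.63² × (1/18 + 1/9) = 0.0662. Pooled gives 0.047, 0.054 and 0.067 at d = 0.1, 0.2 and 0.3. The two are equal at d = 2 × 0.63 × √(1/18) = 0.297.

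**Baseline term.** With equal variances at both visits and correlation r, the residual SD is 0.63 × √((1 + r)/2), and the mean squared error crossover becomes 0.257 (r = 0.5) to 0.289 (r = 0.9). Power at 0.68, pooled v concurrent:

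- r = 0.5: 95.6% v 84.9%
- r = 0.7: 93.1% v 80.3%
- r = 0.9: 90.3% v 75.8%

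The baseline term does not remove drift. At d = 0.3 and r = 0.5 the pooled model with baseline still rejects about 12%; adding cohort brings it back to about 5%.

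**Fisher's test.** Section 2 reports an antibody response "with an increase to 59% after the third dose". Taking 59% detectable as an assumed Cohort 1 rate, exact enumeration of the pooled test with no dose effect gives 2.7%, 2.9%, 5.0% and 11.1% at cohort shifts of 0, 10, 20 and 30 points.

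**1:2 fallback (8.1, 12.3, 14.6).** The mid v standard bias is d × (late share of mid - late share of standard), and it depends on when the high dose stops.

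- After the sentinels: 27 participants remain, giving 9 mid and 18 standard. Groups are 27 v 27; bias = (9/27 - 18/27)d = -d/3.
- After 12 Cohort 2 participants (8 high, 4 standard): 15 remain, giving 5 and 10. Groups are 23 v 23; bias = (5/23 - 14/23)d = -0.39d.
- After 24 (16 high, 8 standard): 3 remain, giving 1 and 2. Groups are 19 v 19; bias = (1/19 - 10/19)d = -0.47d.

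**The case against.** The strongest case is that the planned analysis is a sensible choice and the drift is hypothetical.

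- **Little time to drift.** "The total duration of the study for recruitment and completion of participants is expected to be up to 12 months". With 6 months of follow-up, or up to 7 on study, that leaves about 5-6 months to enrol at one site under fixed eligibility rules. Documented infection is excluded, and Day 1 anti-N positives leave the PP set.
- **The assumed range is generous.** The whole expected standard-dose rise is 0.23, so d of 0.2-0.3 would nearly double it, or more. For the one mechanism tied to the documents, suppose that three- and four-dose recipients differ by the full 0.23 and the mix moves by 50 points: d = 0.23 × 0.5 = 0.115, and the pooled test rejects about 5.7%.
- **That mechanism is a randomisation stratum.** Strata terms in a pooled model would address much of it. How much bias would remain was not computed.
- **Pooling usually wins on accuracy.** Its mean squared error is lower up to about 0.30, and its power at d = -0.2 (76%) still exceeds the concurrent 72%.

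All of this stands, and it is why the concurrent estimate is asked for beside the pooled one and not in its place. It does not remove the gap: change scores do not protect the Day 30 level and detectability tests, for which drift could be larger and is not sized here. The trial is also open-label, and 14.7 allows a look at the Day 30 results, so a choice made afterwards could be driven by the data.

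A reader might infer that the comparison is invalid, or that its false-positive rate is in fact inflated. The documents do not support that, because they give no d. Nor do they support reading 18 v 9 as a sample-size error: 15 per group is correct for the pooled test that the plan specifies.

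**Conclusion.** The point holds as a cheap improvement. Each higher dose is compared with 18 standard-dose participants of whom 9 are concurrent, and nothing in the tests accounts for cohort. The bias is half of any cohort drift, in opposite directions for the two dose contrasts.

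The size rests on an assumed d of 0.1-0.3 log10, normal values with SD 0.63, and equal evaluable controls per cohort. Over that range the pooled t-test's false rejection rises from 5% to at most about 10%. With drift the other way its power falls from 88% to as low as about 68%. Fisher's test stays at or below about 5% up to a 20-point shift and reaches about 11% at 30 points.

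Pooling remains a reasonable main analysis. A reader might also infer that a baseline covariate alone would cure the drift, or that the safety conclusions are at risk. Neither follows: the baseline term leaves the cohort bias in place, and the primary safety analysis is descriptive and does not use these tests.

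**What to change.** In 14.4, 5.2 and the synopsis:

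1. **Main model.** For log10 binding and neutralising values in the randomised PP set, replace the unadjusted t-tests with a linear model on dose, baseline log10 value and the two randomisation strata (number of prior doses, any prior BNT162b2). This is for precision and case mix. With baseline in the model, Day 30 level and change give the same dose estimate.
2. **Sensitivity analysis beside it.** Prespecify the same model with a cohort term, plus Fisher and rank tests restricted to the relevant cohort (Cohort 2 for high, Cohort 1 for mid). Report the estimate and 95% interval. State whether it has the same direction as the pooled estimate and an interval compatible with it. Do not use its p-value as a gate.
3. **Fallback.** Use the cohort term in the 1:2 fallback too.
4. **Section 14.6.** Keep 15 per group and add that the concurrent comparison is 18 v 9 with about 72-74% unadjusted power, against 88% for 18 v 18 pooled.
5. **Timing.** The sponsor fixes in writing which version is the main analysis before Day 30 data are seen.

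**Cost.** No new participants or samples; baseline blood, strata and cohort are already recorded. The gain from the baseline term, pooled power of 90-96%, assumes normality, equal variances and correlation of 0.5-0.9. Many baselines at the LLOQ would weaken it. The downside is a second, less precise estimate (11-15 power points lower with the baseline term) and more secondary results to report.

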5.2 Secondary Immunogenicity Endpoints

1. **Binding antibody:** The anti-RBD and anti-spike (S-2P) IgG concentrations (log10 and geometric mean concentrations (GMC)) at Day 30 will be evaluated with comparisons between the standard-dose versus high-dose groups. T-tests with two-sided $p<0.05$ significance will be used (overall α level of 0.1). Changes in the anti-RBC and anti-spike IgG concentrations at Day 30 will be compared pairwise between the standard-dose versus high-dose groups using two sample T-tests with two-sided $p<0.05$ significance (overall α level of 0.1). The percent of participants with detectable antibody levels (greater than the LLOQ) at Day 30 will also be evaluated using Fisher's exact tests. Pairwise comparisons of binding antibodies will also be evaluated between the standard-dose versus mid-dose groups.
2. **Neutralizing antibody:** Neutralizing antibody titers (geometric mean titers (GMT)) from a pseudovirus neutralization assay at Day 30 will be compared between the standard-dose versus high-dose groups using T-tests with two-sided $p<0.05$ significance (overall α level of 0.1). Changes in the neutralizing antibody titers at Day 30 will be compared between the standard-dose versus high-dose groups using two sample T-tests with two-sided $p<0.05$ significance (overall α level of 0.1). The percent of participants with detectable neutralizing antibody levels (greater than the LLOQ) at Day 30 will also be evaluated using Fisher's exact tests. Pairwise comparisons of neutralizing antibodies will also be evaluated between the standard-dose versus mid-dose groups.
3. **Cellular immunogenicity:** The change in the frequency of target cytokine producing T-cells by flow cytometry with intracellular staining at Day 30 will be compared using the Kruskal-Wallis Test for standard-dose versus high-dose groups. A comparison of T-cell frequencies between the standard-dose versus high-dose groups will be evaluated using the Wilcoxon rank-sum test. Pairwise comparisons of cellular immunogenicity will also be evaluated between the standard-dose versus mid-dose groups.

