6.2 Inclusion Criteria

1. All adult lung transplant recipients (age ≥ 18 at the time of consent) who received all of their COVID-19 vaccines after lung transplantation.
2. Received three or four doses of either the Moderna mRNA-1273 or Pfizer BNT162b2 vaccine with the last dose received at least 4 months prior to study enrollment.
3. Currently receiving standard regimen of three drug immunosuppression with prednisone, tacrolimus and mycophenolate mofetil (minimum 250 mg bid) or mycophenolate sodium (minimum 180 mg bid).

4. Agrees not to receive other investigational agents for prophylaxis against COVID-19 including Evusheld monoclonal antibodies for at least 30 days after the study vaccine.
5. Understands and agrees to comply with the study procedures and provides written informed consent.
6. Is in stable health without any new or worsening medical conditions in the opinion of the Investigator.
7. Female participants of childbearing potential (<1 year since start of menopause) may be enrolled in the study if the participant fulfills all the following criteria:
 - a. Has a negative pregnancy test at Visit 1 Day 1.
 - b. Has practiced adequate contraception or has abstained from all activities that could result in pregnancy for at least 28 days prior to the first injection (Day 1).
 - c. Has agreed to continue adequate contraception or practice abstinence through 3 months following the booster injection (Day 90).
 - d. Is not currently breastfeeding.
 - e. Adequate female contraception is defined as consistent and correct use of a Food and Drug Administration (FDA) approved contraceptive method in accordance with the product label. For example:
 - i. Barrier method (such as condoms, diaphragm, or cervical cap) used in conjunction with spermicide
 - ii. Intrauterine device
 - iii. Prescription hormonal contraceptive taken or administered via oral (pill), transdermal (patch), subdermal, or IM route
 - iv. Sterilization of a female participant's monogamous male partner prior to entry into the study
 - v. Note: periodic abstinence (e.g., calendar, ovulation methods) and withdrawal are not acceptable methods of contraception.

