14.6 Sample Size Justification

The overall mean \log_{10} IgG increase after the third (100 ug) vaccine dose was 0.46 with standard deviation (SD) 0.63. Assuming participants have a 50% lower response to the 50 ug fourth-dose, the expected mean \log_{10} IgG increase is 0.23. Assuming participants have a 100% higher response to the 200 ug fourth-dose, their expected mean \log_{10} IgG increase is 0.91. For 80% power to detect this difference between high-dose and standard-dose groups with a SD of 0.63 for a two-sample t-test with two-sided $\alpha<0.05$ significance, the minimum required sample size is 15 per group. Thus, we will enroll 20 participants in each group. The first 2 participants in the mid and high-dose groups will be enrolled as the sentinel group to ensure an acceptable safety profile before the full group is enrolled.

If the halting criteria is triggered for the high-dose group and further enrollment of this group is not recommended by the study investigators, DSMB or IRB, the study will continue randomized enrollment into the mid-dose and standard-dose groups with a 1:2 ratio to complete the enrollment of 60 participants total. Since the expected immunogenicity difference between the mid-dose and standard-dose group is smaller, we will require more participants to detect a difference between these two groups. The 1:2 enrollment ratio into the mid-dose and standard-dose groups will even the distribution of participants into these two groups. The primary endpoint analysis for safety and reactogenicity will not be affected by a restriction of participants into the mid-dose and standard-dose groups.

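### The Day 30 percent-detectable analysis ignores Day 1 antibody status, so carried-over vaccine antibody dilutes the dose contrast and can be misread as booster response

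*Combined protocol and SAP*

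**What the plan says.** Sections 5.2 and 14.4 and the synopsis define a binary summary for each humoral assay. For binding antibody it is "The percent of participants with detectable antibody levels (greater than the LLOQ) at Day 30", and for neutralising antibody "The percent of participants with detectable neutralizing antibody levels (greater than the LLOQ) at Day 30". Both are compared by Fisher's exact test, with no condition on the Day 1 result. A two-sided 0.05 level is given for the t-tests ("T-tests with two-sided $p<0.05$ significance will be used"). No level, expected rate or power is given for the Fisher tests.

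On who enters, section 6.2 item 2 reads "Received three or four doses of either the Moderna mRNA-1273 or Pfizer BNT162b2 vaccine with the last dose received at least 4 months prior". Neither section 6.2 nor 6.3 sets an antibody-negative or low-titre criterion. Section 2 reports a single-centre cohort in which 35% had an anti-RBD response after dose two, "with an increase to 59% after the third dose".

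Three other provisions bear on the point:
- Section 4.1 stratifies randomisation by number of prior doses and prior BNT162b2, not by serostatus.
- Section 14.1 removes participants with anti-N antibody from the per-protocol set. That deals with past infection, not vaccine antibody.
- Section 10.2 item 12 draws Day 1 blood for the same antibody assays.

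**The concern.** Someone already above the LLOQ on Day 1 will often still be above it on Day 30 whatever the dose. Such participants enter both numerator and denominator and say little about the booster. Two things follow. The difference between doses is compressed toward the share who could still change status. And a reader who sees a high Day 30 percentage may credit the booster with antibody that earlier doses produced. Section 2.1 argues that the 50 ug booster will not be enough for many recipients, so the natural binary question is whether a higher dose brings people without antibody above the LLOQ. The planned percentage does not isolate them, although the Day 1 sample needed to do so is already collected.

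**Working it through.** **The plan's own figure.** Section 14.6 sizes the trial on the log10 IgG increase: 0.23 (50 ug) v 0.91 (200 ug), SD 0.63, two-sided 0.05, 80% power. The normal approximation gives n = 2 × (1.96 + 0.84)² × (0.63/0.68)² ≈ 13.5, so 14 per group. The noncentral t gives 14.50, so 15, which matches the plan. Power is 0.81 at 15 and 0.88 at 18 per group. This calculation uses the increase, so carry-over does not affect it.

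**Inputs for the binary endpoint.** The per-protocol set has 18 high-dose and 9 + 9 = 18 standard-dose participants (sections 4.1 and 14.1). Baseline positivity q = 0.59 is the section 2 proxy, varied from 0.40 to 0.75. The following are assumptions because the documents do not give them: a two-sided 0.05 level for Fisher's test, the conversion rates c among Day 1 negatives, and the baseline spread.

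**Model A: positives stay positive.** The Day 30 rate is q + (1 − q)c, so the dose difference is (1 − q)(c_high − c_std). With q = 0.59 and c of 20% v 80%, the rates are 67% v 92%. The difference is 0.41 × 0.60 = 0.25, against 0.60 among the negatives. About 18 × 0.41 ≈ 7 per group are negative. Simulated power (within about 0.01), planned Fisher test v Fisher test in Day 1 negatives only:

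| Day 1 positive | 20% v 60% | 20% v 80% | 10% v 80% |
|---|---|---|---|
| 40% | 0.22 v 0.38 | 0.55 v 0.76 | 0.69 v 0.91 |
| 59% | 0.12 v 0.23 | 0.32 v 0.53 | 0.43 v 0.71 |
| 75% | 0.06 v 0.10 | 0.13 v 0.26 | 0.19 v 0.38 |

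The ratio runs from 0.13/0.26 = 0.50 to 0.69/0.91 = 0.76.

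**Model B: positives may fall below the LLOQ.** Day 1 log10 concentration is normal, with its mean set so that a share q exceeds the LLOQ. The section 14.6 increases (0.23 or 0.91, SD 0.63) are added independently of baseline. At q = 0.59:

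| Assumed baseline SD | Planned test | Negatives only |
|---|---|---|
| 0.5 | 0.27 | 0.18 |
| 0.8 | 0.18 | 0.16 |
| 1.0 | 0.14 | 0.14 |
| 1.5 | 0.085 | 0.097 |

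With baseline SD 0.5, the planned test has 0.19 v 0.07 for negatives only at q = 0.75, and 0.33 v 0.30 at q = 0.40. The reversal arises because baseline-positives, mainly at standard dose, drop below the LLOQ and so carry dose information. If such losses are forbidden in the same model (q = 0.59), the order returns: 0.12 v 0.18 at SD 0.5 and 0.08 v 0.14 at SD 1.0.

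**Reading of the percentages.** In Model B at q = 0.59 and SD 0.5, 17% of standard-dose positives are lost and 66.5% are detectable on Day 30. So 0.59 × 0.83 / 0.665 ≈ 74% of those counted as detectable were already so on Day 1. Over SD 0.5 to 1.5 the share is about 74% to 86% at standard dose and 64% to 75% at high dose.

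**All participants, stratified by Day 1 status.** An exact conditional test over the two Day 1 strata had higher power than the planned test in all 27 scenarios run across both models. Examples at q = 0.59, stratified v planned:
- Model A, conversion 20% v 80%: 0.53 v 0.32. Here it coincides with the negatives-only test, because the positive stratum has no variation.
- Model B, SD 0.5: 0.33 v 0.26.
- Model B, SD 1.0: 0.21 v 0.14.

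**The case against.** The strongest reply is that this is a supportive analysis and carry-over is already handled where inference matters. Safety is primary, section 14.4 also tests change from baseline, and the only power statement ("For 80% power to detect this difference between high-dose and standard-dose groups") concerns the increase. The share of recipients with detectable antibody after each dose is also a legitimate practical quantity, and section 3.2 asks only for humoral immunogenicity. All of this stands, and it limits the weight of the point.

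A reader might infer that ignoring Day 1 status halves the endpoint's power. The documents do not support a single figure. They give no Day 1 positivity, no conversion rate by dose and no power for this endpoint. The 59% is anti-RBD after dose three, whereas entrants are at least 4 months past their last dose and some have had four. No comparable figure exists for anti-spike or neutralising antibody.

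A reader might also infer that the endpoint should simply be replaced by conversion among Day 1 negatives. Model B shows that this can lose power, so outright replacement is a trade-off.

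Finally, a reader might infer bias. Randomisation within each cohort balances Day 1 positivity in expectation, and Fisher's test allows for chance imbalance. A gap of 4 or more of 18 in Day 1 positivity would arise by chance in roughly 18% to 24% of trials under simple randomisation, and the planned stratification may reduce that. This is noise, not systematic error.

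**Conclusion.** The point holds as a matter of dilution and interpretation in a supportive secondary analysis. Day 1 antibody is measured but not used, and nothing in entry, stratification or the anti-N exclusion deals with vaccine-derived antibody. The planned test keeps about 50% to 76% of the power of a negatives-only analysis if Day 1 positives stay positive, with 40% to 75% positive at baseline and 18 v 18. If positives near the LLOQ can fall below it, a negatives-only test may have equal or lower power. What does not depend on that choice is that, in every scenario run, keeping everyone and stratifying by Day 1 status did better than the planned test. The change-from-baseline t-tests and the 15-per-group calculation are unaffected. The change is worth making, but the trial's validity does not depend on it.

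**What to change.** In section 5.2, section 14.4 and the synopsis, for anti-RBD, anti-spike and neutralising antibody:
- Keep all per-protocol participants, but replace the unstratified Fisher test with an exact conditional test stratified by Day 1 detectability on the same assay, for standard v high and standard v mid. State its significance level.
- Report Day 30 detectability by dose and Day 1 status. Include conversion, defined as above the LLOQ on Day 30 among those at or below it on Day 1.
- Keep the all-participant percentage as a description, labelled as prevalence of detectable antibody and not as response to the booster.

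The cost is wording and a little more analysis. No new samples, visits or participants are needed. The conversion subset will be small (about 7 per group if 59% are positive on Day 1), so its estimates will be imprecise and should be shown with exact confidence intervals. Because the trial is open-label, the change is best fixed in writing before Day 30 results are examined.
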